1.2 SCHEDULE OF ACTIVITIES (SOA)

Procedures	Screening and randomization Days -1-5	Enrollment/Baseline Days 2-5 till discharge from NSCU	Step down unit Neurosurgical floor	Final Study discharge
Informed consent	Х			
Demographics	х			
Medical history	Х			
Administer study intervention		Х	x	
Concomitant medication review	х	Х	х	x
Physical exam (including height and weight)	х	Х	x	х
Vital signs (temperature, BP, HR, Oxygen saturation)	х	Hourly and as needed	x	х
Height	Х			
Weight	Х	Х		Х
Performance status	Х	Х	x	Х
Hematology	Х	Х	x	
serum chemistry	Х	Х	X	
Pregnancy test	Х			
EKG (as indicated)	Х	х	As needed	
Daily narcotic use	х	х	x	
Adverse event review and evaluation	х	х	x	x
Radiologic/Imaging assessment (CT, MRI, CTA/CTP, angiogram)	х	х	x	x
Patient satisfaction assessment				x
Complete Case Report Forms (CRFs)	х	х	x	Х

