2.3.2 KNOWN POTENTIAL BENEFITS

gammaCore has been successfully studied for the acute and preventive treatment of cluster and migraine headache.(19) It has been proven to decrease headache intensity, and prevent migraine attacks. To this point it has not been studied in patients with headache due to SAH. Given the shared pathophysiology (inflammation, cortical spread depression) and the potential of deactivating the nociceptive center, nVNS could potentially alleviate SAH related headache, decreasing the usage of opiates and steroids and thereby decreasing their side effects. This could potentially decrease the ICU and hospital length of stay, decrease the readmission rate from headache due to SAH, decrease the outpatient usage of opiates and prevent opiate dependency.

In addition, nVNS could also provide neuroprotection against stroke, one of the most feared complication in a-SAH. Stroke in a-SAH is thought to be due to vasospasm of blood vessels caused by inflammation and cortical spreading depression leading to ischemia. In animal model, noninvasive VNS has been shown to significantly reduce CSD.(11) In addition, nVNS has anti-inflammatory properties. Experimental animal studies have shown that VNS has the potential of improving outcome in critical illnesses through its anti-inflammatory effects which could potentially extend to sepsis, intracranial hemorrhage, ventilator related lung injury, postoperative cognitive dysfunction, myocardial ischemia and reperfusion injury. One of the postulated mechanisms, is that it regulates α 7nAChR which regulates inflammation.(23) Animal studies have shown that stimulating the α 7nACh decreases inflammatory markers.(24) Through inhibiting CSD and controlling inflammation, nVNS could potentially prevent secondary brain injury (strokes and DCI) seen in a-SAH patients.

Studies have also shown that VNS enhances neuroplasticity, which could fasten recovery. Animal studies on intracranial hemorrhage showed that VNS improves functional recovery.(25) Multiple ongoing studies are evaluating the beneficial effects of VNS in improving functional recovery during rehabilitation of patients with strokes.(22) nVNS could potentially help recovery from SAH.

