8 STUDY ASSESSMENTS AND PROCEDURES

8.1 EFFICACY ASSESSMENTS

Per standard of care, patients presenting with signs of SAH like acute severe headache, will get a diagnostic head CT which confirms blood in the subarachnoid space. If patients have symptomatic hydrocephalus (altered mental status with CT head consistent with hydrocephalus) an external ventricular drain will be placed. Most patients will get either a CT angiogram or a conventional angiogram to rule out a vascular malformation, especially if there is no history of trauma. If an aneurysm is detected, the standard of care is to treat it as soon as possible. Usually, an aneurysm iseither coiled or clipped (craniectomy or craniotomy). Every patient admitted with subarachnoid hemorrhage will get graded accordingly to their headache intensity, level of consciousness and neurologic deficits with the Hunt Hess grade (table 2). Their CT scans also get graded (modified fisher scale mFS) according to the thickness and location of blood (table 3). All subarachnoid hemorrhage (unless there is minimal amount of blood and no vascular malformation) are admitted to the Neurosurgical care unit (NSCU). Detailed physical examination, including the NIHSS, history, including medication history, past medical, surgical history, and social history are recorded in the medical records. North Shore University hospital NSCU is the referral center for most of the hospitals in Northwell health care system. Most aneurysmal SAH patients get transferred to our unit. Per standard of care, all women of child bearing age, admitted to the NSCU get a urine or blood pregnancy test, patients suspected of abusing drugs get urine toxicology. Once in the NSCU, patients get vital signs and neurologic assessment every hour, and pain assessment every 4 hours and as needed. The length of stay in the intensive care unit depends on the amount of blood on the head scan (mFS). Patients with higher mFS are more prone to get delayed cerebral ischemia. As a result, per standard of care, patients with SAH get almost daily transcranial dopplers to monitor for cerebral vasospasm, frequent head scans, occasionally brain perfusion studies and MRI of the brain. Patients are monitored for central fever (vital signs, blood cultures), cerebral salt wasting with frequent BMP and urine output measurements, seizures with PRN electroencephalograms (EEG). Once out of the critical care period, (vasospasm usually starts at day 3 post bleeding and peaks at day 10), patients get transferred to a regular neurosurgical floor before being discharged home or to rehabilitation. On average patients stay in the NSCU between 2-21 days. All patients admitted to the NSCU with SAH will be screened and evaluated for the inclusion and exclusion criteria after obtaining an informed consent.

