
Screening involves reviewing the medical records following HIPPA regulation for: Age, gender, ethnicity, presence of aneurysm, day of rupture, etiology of the SAH if not aneurysmal, radiologic (Angiogram, CT head) and medical history before and after the aneurysm is secured, Glasgow coma score before and after aneurysm repair, modified fisher scale (mFS), Hunt-Hess grade (HHS), time of ictus, history of alcohol and drug abuse, presence of hydrocephalus on head CT, presence of an external ventricular drain (EVD), date of EVD placement, new HHS after EVD placement, clipping or coiling. Medical records will be reviewed for the past medical history (pacemaker, defibrillator, history of CHF, arrhythmias, cervical carotid disease, history of a headache disorder like migraine or cluster headache), physical examination, labs will be reviewed which includes but not limited to pregnancy test and urine toxicology. Headache intensity and opiate, steroids and acetaminophen usage are recorded in the electronic medical record. The presence of vasospasm and delayed cerebral ischemia will be noted. Once found eligible satisfying the inclusion and exclusion criteria, and informed consent signed, patients will be randomized to either the treatment group or the control group. The same data will be recorded for both groups. The treatment period will start once admitted in the NSCU and will last for up to 10 days.

During the NSCU stay, patients areevaluated for pain every 4 hours. If vital signs are stable (SBP> 100 mmHg and HR> 60 beats per minutes with no arrhythmia on telemetry, MAP> 60 mmHg and oxygen saturation > 90%) patient will receive either the treatment (nVNS) or the Sham device every 5 hours. Headache intensity will be evaluated every four hours. In addition, vital signs will be noted just after stimulation, and hourly afterwards or as ordered by the physician. The daily mean morphine equivalence dosage will be recorded. Concomitant medications will be recorded.

During the ICU length of stay, the following will be assessed and recorded per standard of care :

- Transcranial dopplers (TCD)
- Neuroimaging (CT head, MRI brain, angiograms, CT perfusion with permeability study)
- EVD weaning and day of start of weaning
- Presence of vasospasm, delayed cerebral ischemia, Central fever, Cerebral salt wasting. These are usually recorded in the medical record.
- Urinary retention documented as frequent straight catheterization for more than 3 days

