- Constipation evaluated by the need for enema, suppository, lactulose or magnesium oxide administered
- Blood tests, CSF studies
- EEG results
- Neurologic examination including Glasgow coma score, and NIHSS
- Delirium score

When Transcranial dopplers are being done as per standard of care, we will assess the changes in transcranial velocities around the time of the stimulation of the Vagus nerve.

When possible, we will draw blood or in case there is an EVD we will also collect CSF for biomarkers. Not more than 5 ml of blood will be drawn before the 11:30 am stimulation session of the Vagus nerve. This will be repeated approximately 24 hours later, at 11:30 am post VNS stimulation session. This might be repeated on days 5 and 7 post-ictus In case there is an EVD, 2 cc of CSF from the drain and 20 cc of CSF that is otherwise discarded will be drawn before the 11:30 am stimulation session of the Vagus nerve. Another 2 cc of CSF from the drain and 20 cc of CSF that is otherwise discarded will be drawn before the 11:30 am stimulation session of the Vagus nerve. Another 2 cc of CSF from the drain and 20 cc of CSF that is otherwise discarded will be drawn approximately 24 hours later, at around 11:30 am post VNS stimulation session. This might be repeated on days 5 and 7 post-ictus.

The CSF will not be taken from the proximal port of the EDV unless it is being tested for CSF cell count or cultures as per standard of care. This is in order not to increase the risk of infection.

Deidentified blood and CSF will be sent to [name], academic chief in the department of stroke and vascular neurology, Yale, [name].

IF CT perfusion is being performed per standard of care between days 3-10, blood brain permeability will be evaluated and results will be compared between the sham group and the active device group.

During the period of the study after the patients are discharged from the ICU to the Neurosurgical floor, we will evaluate their daily headache intensity and morphine equivalence dosage, in addition to their TCD results, Neuroimaging and EEG results, neurologic examination and vital signs.

Table 2: Hunt-Hess Score in aneurysmal SAH: (26, 27)

- 1. Asymptomatic, mild headache, slight nuchal rigidity
- 2. Moderate to severe headache, nuchal rigidity, no neurologic deficit other than cranial nerve palsy
- 3. Drowsiness, confusion, mild focal neurologic deficit
- 4. Stupor, moderate-severe hemiparesis
- 5. Coma, decerebrate posturing

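### Urinary retention and constipation are defined only in the ICU assessment list, so how fully they are counted depends on ICU days, and the planned proportions take no account of days observed

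*Protocol*

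**What the plan says.** - **Endpoint.** The objectives table in protocol section 3 makes opioid-related adverse events a secondary endpoint, counted as the number of patients with each of seven events: urinary retention, constipation, sedation, nausea, respiratory depression, vomiting and pruritus.
- **Definitions.** Protocol 8.1 opens a list with "During the ICU length of stay, the following will be assessed and recorded per standard of care". That list contains "Urinary retention documented as frequent straight catheterization for more than 3 days" and "Constipation evaluated by the need for enema, suppository, lactulose or magnesium oxide administered". The SAP reproduces it after its schedule table. Neither document defines these two events anywhere else.
- **Floor.** For the period after ICU discharge, 8.1 says "we will evaluate their daily headache intensity and morphine equivalence dosage, in addition to their TCD results, Neuroimaging and EEG results", followed by neurologic examination and vital signs. Retention and constipation are not named.
- **General safety capture.** In the schedule (protocol 1.2), the row "Adverse event review and evaluation" is marked in every column, including the floor and final discharge. So is concomitant medication review. The SAP schedule agrees. Protocol 8.3.3 requires all adverse events during the study to be documented. It records reportable events until 3 days after the last stimulation or hospital discharge, whichever is first.
- **Analysis.** Protocol 9.4.4 reports opioid-related events as proportions with exact 95% binomial intervals. By contrast, 9.4.3 adjusts total morphine equivalent dose for the number of days in study.
- **ICU stay.** Protocol 8.1: "On average patients stay in the NSCU between 2-21 days". Protocol 2.3.2, on the hoped-for benefits of stimulation: "This could potentially decrease the ICU and hospital length of stay".

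**The concern.** A proportion of patients with an event rises with the time over which the event is looked for. If the two definitions are applied only in the ICU, a patient who moves early to the floor has fewer days on which to be counted, even though treatment and opioid use may continue there. If floor events are also counted, but through general adverse event recording, two different rules feed one endpoint. Either way, the count depends partly on where the patient is.

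Two things are at stake. First, the rates may be too low in both arms, in a pilot meant to inform a larger trial. Second, if one arm has fewer ICU days after randomisation, it will show fewer recorded events for that reason alone. The analysis has no term for days observed that would reveal or correct this.

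**Working it through.** The documents give no event rate or ICU-stay difference for this endpoint, so there is no figure of the plan's own to reproduce. The check is a reading of the text followed by an illustration.

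**Text, side by side**

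| Item | ICU | Floor |
|---|---|---|
| Opioid dose | recorded | recorded (8.1) |
| Retention and constipation, as defined | listed (8.1, SAP) | not listed |
| General adverse event and medication review | yes (1.2) | yes (1.2) |
| Statement that floor events count towards the endpoint | – | none |

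**Illustration.** Assumptions, none of them from the documents: a constant daily onset risk *h*, equal in both arms; *L* ICU days after randomisation; no floor event counted (the extreme case).

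Constipation has no minimum duration, so P(recorded) = 1 − (1 − h)^L.
- h = 0.05: 8 days, 1 − 0.95^8 = 0.337; 6 days, 1 − 0.95^6 = 0.265; gap 0.072.
- h = 0.10: 8 days, 1 − 0.90^8 = 0.570; 6 days, 1 − 0.90^6 = 0.469; gap 0.101.
- Equal *L* in both arms: gap 0 at any *h*.

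Retention needs more than 3 days, that is, at least 4 ICU days including the day of onset, if the episode persists. So P(recorded) = 1 − (1 − h)^max(0, L − 3).
- L of 3 or fewer: 0 at any *h*, if only post-randomisation ICU days count.
- h = 0.05: 8 days, 1 − 0.95^5 = 0.226; 6 days, 1 − 0.95^3 = 0.143; gap about 8 points.
- h = 0.10: 8 days, 1 − 0.90^5 = 0.410; 6 days, 1 − 0.90^3 = 0.271; gap about 14 points.

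**Wider range.** For 7 versus 10 ICU days and *h* from 0.02 to 0.10, the gap is 5 to 13 points for constipation and 5 to 18 for retention. With 20 patients per arm (40 randomised 1:1), a two-sided Fisher test at 0.05 would reject in 3% to 12% of trials. The distortion would therefore appear mainly in the point estimates and seldom as a significant result.

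**Chance imbalance.** Protocol 8.1 ties ICU stay to the amount of blood on the scan, and no stratification is stated. With an assumed SD of 3 ICU days, the standard error of the difference in mean stay is 3 × √(2/20) = 0.95 days. A difference above 1 day in either direction then arises by chance about 29% of the time. This adds noise but does not systematically favour one arm.

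**With one common window.** If every patient is observed for 10 days on ICU and floor alike at h = 0.05, the expected rates are 1 − 0.95^10 = 0.401 for constipation and 1 − 0.95^7 = 0.302 for retention in both arms. The gap is zero.

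**The case against.** The strongest reply is that the plan nowhere confines these events to the ICU. Adverse event and medication review run to final discharge, all adverse events in the study must be documented, and protocol 4.4 continues data collection to hospital discharge. Constipation is defined by agents that a medication review would be expected to show. The floor list is plainly not exhaustive: it also omits blood tests that the schedule marks for the floor. All this stands. A reader might infer that retention and constipation are assessed only in the ICU, but the documents do not say so. What they leave open is whether the same definitions apply on the floor and whether floor events count.

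A reader might also infer that a shorter ICU stay favours active stimulation by construction. It does not: the gap is zero when stays are equal. Protocol 8.1 says stay depends on the amount of blood, which is fixed before randomisation. The sections on potential benefits link a shorter stay to lower opioid use, and in that case part of any recorded fall in events would be real.

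Three further limits also stand.
- Only two of the seven events are in the ICU list, and the more-than-3-day rule affects only retention, so the opioid-harm rate as a whole is not shown to be distorted.
- It is tempting to say that opioid dose and opioid harms cover different periods. The documents are not uniform on this: protocol 9.4.2 analyses daily dose during the NSCU stay, while the SAP analyses it to Day 14.
- The zero for retention supposes that only post-randomisation ICU days count. The text speaks of the ICU stay, and nothing says that catheterisation begun there stops counting on the floor.

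Finally, these are descriptive comparisons in a pilot without statistical hypotheses.

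**Conclusion.** The point holds as an unreconciled window and definition for two of the seven opioid-related events. Followed as written, the two lists make ascertainment depend on ICU days. General adverse event recording may fill the gap, but not by a stated rule, and the crude proportions cannot show whether it did. Rates are understated for patients with short ICU stays to the extent that floor events go uncounted.

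A difference between arms needs unequal post-randomisation ICU days. The protocol regards a shorter stay as possible but gives no figure. The illustrative size is 7 to 10 points for constipation at 6 versus 8 ICU days, with no true effect. It rests on assumed daily risks of 5% to 10%, an assumed stay difference, and no floor events being counted. The documents do not establish that any such bias will occur. Even so, the matter is more than missing detail, because the remedy is specific and cheap. The daily opioid dose endpoint is not affected.

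**What to change.** In protocol 8.1 and the matching SAP list, apply the same retention and constipation definitions on ICU and floor. Run them from first stimulation to the end of the study period or hospital discharge, using the electronic medication and nursing records. State that events in either setting count towards the secondary endpoint.

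Hospital discharge is not a fully common end, since the protocol suggests that stimulation may shorten hospital stay too. In protocol 9.4.4 and the SAP safety section, therefore, report observed days at risk per arm and the event rate per patient-day beside the proportions and their exact intervals.

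The cost is a wording change in both documents and some extra chart extraction on the floor. Protocol 10.1.8 says that most study data already come from the electronic medical record, so no new patient procedure is needed.

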The difference in cytokines levels and blood brain permeability markers in the blood and/or CSF before and after stimulation and between the sham and active group	When possible, cytokines levels and permeability markers will be measure in the blood and/or serum just before the first vagus nerve stimulation and approximately 24 hours later, after the 11:30 AM stimulation session. If possible, this will be repeated on day 5 and 7 post-ictus as it is the period of cerebral vasospasm

	Immunologic investigations include but not limited to, measurement of inflammatory protein levels, RNA		
	sequencing of leukocyte and stimulation assays.		
Evaluate the effects of VNS on	The integrity of the blood brain barrier will be evaluated		
blood brain barrier integrity	through CT perfusion if performed as standard of care.		
Exploratory objectives			
Comparisons of the rates of stroke, vasospasm, DCI, seizure, and central fever between the active and sham treatment groups	Neuroimaging upon admission and at discharge will be compared and evidence of new strokes will be noted. The presence of DCI (change in neurologic examination thought to be due to vasospasm) will be evaluated.		
	Transcranial doppler velocities will be compared between the active and sham groups		
	The number of days with central fever will be compared between the active and sham groups		
	Incidence of seizures will be compared between the active and sham groups		
Effect of nVNS on severity of cerebral vasospasm during DSA	Rate of change in the severity of cerebral vasospasm will be noted before and during or after nVNS		

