4.4 END OF STUDY DEFINITION

The study intervention will be up to 10 days in length. Vagus stimulation will be performed 4 times daily (approximately at 6:30AM, 11:30AM, 4:30PM and 9:30PM). Data collection will continue till hospital discharge. If the participant becomes hemodynamically unstable, defined as hypotension requiring vasopressors the VNS will be held for safety purposes. However, it will be resumed, once the patient is stabilized, off vasopressors for 48 hours. If the patient is being hemodynamically augmented for symptomatic vasospasm, n-VNS will not be withheld as the beneficial effects of n-VNS on symptomatic vasospasm will be investigated in this study.

Participants must fulfill all of the inclusion criteria in order to be eligible for the study:

- Established signed and dated informed consent form
- Can be enrolled within 5 days of cerebral aneurysm treatment.
- CT of the head revealing blood in the subarachnoid space
- Subject has ruptured cerebral aneurysm or SAH patients who do not have vascular malformation on cerebral angiogram.
- Subject is male or female 18 -75 years of age
- Subject is alert able to verbalize pain at the time of enrollment
- Subject reports pain of 7 and greater on a 10 Point Pain numeric rating scale or presenting with severe headache.
- Female of reproductive age must have a negative pregnancy test (Urine or blood test)

nVNS will only be performed if vital signs are stable (HR>60, SBP> 100 mmHg, MAP> 60 mmhg, and saturation > 90% on room, nasal cannula or face mask). Then the vagus nerve will be stimulated.

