5.5 STRATEGIES FOR RECRUITMENT AND RETENTION

The neurosurgical critical care unit (NSCU) at Northshore University Hospital is the main referral unit for the healthcare system for patients with subarachnoid hemorrhage. All transferred patients

are admitted to the NSCU, as a result, patients can be easily identified by the research team on a daily basis. Every day, the neurointensivist or the research coordinator will evaluate which patients admitted to the NSCU have been diagnosed with subarachnoid hemorrhage. If an aneurysm is found to be the cause of the SAH, surgical or endovascular treatment of the aneurysm is typically performed within 72 hours of diagnosis. Patients will be included in the study once the aneurysm has been treated. The primary investigator, or sub investigators will take consent from the patient. The primary investigator will ensure that the sub investigators and research assistants are trained and knowledgeable of the research protocol. Patients enrolled in the study will be followed up to 10 days starting 24 hours post successful treatment of the aneurysm unless discharged earlier from the hospital.

We admit on average 110 SAH cases a year. If we assume that 50% satisfy our inclusion criteria, and that 70% will sign the inform consent, we should be able to reach our target number in approximately 12 months. Patients identified in the NSCU will be approached by the research team, and the study will be explained to them.

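### Protocol 3 and 8.1 define the pre-stimulation biomarker sample differently, so a baseline drawn under 8.1 may follow up to three sessions, and some later values may precede the first one

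*Protocol*

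**What the plan says.** Protocol 3 lists as a secondary objective the difference in cytokines and permeability markers "before and after stimulation and between the sham and active group". Its endpoint column times the two core samples "just before the first vagus nerve stimulation and approximately 24 hours later, after the 11:30 AM stimulation session" and adds an optional extension: "If possible, this will be repeated on day 5 and 7 post-ictus as it is the period of cerebral vasospasm".

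Protocol 8.1 gives the collection instruction. For blood it says "Not more than 5 ml of blood will be drawn before the 11:30 am stimulation session of the Vagus nerve", and then "This will be repeated approximately 24 hours later, at 11:30 am post VNS stimulation session". CSF follows the same rule, with the pre-session draw printed twice. The day 5 and day 7 repeats are again optional. For imaging, "IF CT perfusion is being performed per standard of care between days 3-10, blood brain permeability will be evaluated"; the origin of that day count is not given.

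Sessions run at about 6:30 AM, 11:30 AM, 4:30 PM and 9:30 PM (Protocol 4.4 and 6.1.2). Neither section says which of these is a patient's first.

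On entry, one inclusion criterion (printed after Protocol 4.4) reads "Can be enrolled within 5 days of cerebral aneurysm treatment", and Protocol 5.5 says that "surgical or endovascular treatment of the aneurysm is typically performed within 72 hours of diagnosis".

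The schedule of activities (Protocol 1.2) has no row for biomarker samples. The SAP defines baseline as the Day 1 value (General approach) and compares arms at each visit by t-test (Analysis of Secondary and Exploratory Variables). Neither rule refers to the first stimulation.

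**The concern.** A before/after objective needs a first sample that is free of the intervention. Protocol 3 asks for one. Protocol 8.1, the text that staff would follow when collecting, anchors the draw to a clock slot that need not be the patient's first. If the two differ for a given patient, the active-arm baseline already carries some stimulation, and any early effect of that stimulation is subtracted from the change being measured. In the sham arm the earlier sessions deliver no stimulation, so the active-minus-sham difference in change could be pulled toward zero.

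A second, smaller issue is that follow-up values and exposure run on different clocks. The day 5 and day 7 draws count from ictus, while enrolment counts from aneurysm treatment. A value obtained before the first session says nothing about stimulation, but a by-visit comparison would include it as if it did. Nothing in the SAP separates exposed from unexposed values.

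**Working it through.** The plan gives no figure to reproduce, so the check is timeline arithmetic.

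**1. Sessions already given at the 8.1 baseline draw.** Inputs: the four session times (Protocol 4.4, 6.1.2), the draw before the 11:30 session and the second draw a day later after the 11:30 session (8.1). For each possible first session, count sessions up to the next 11:30 draw. Each session is two two-minute stimulations.

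| First session | Sessions before the baseline draw | Two-minute stimulations | Sessions by the second draw | Sessions between draws |
|---|---|---|---|---|
| 11:30 AM | 0 | 0 | 5 | 5 − 0 = 5 |
| 6:30 AM | 1 (6:30 AM) | 2 | 6 | 6 − 1 = 5 |
| 9:30 PM | 2 (9:30 PM, 6:30 AM) | 4 | 7 | 7 − 2 = 5 |
| 4:30 PM | 3 (4:30 PM, 9:30 PM, 6:30 AM) | 6 | 8 | 8 − 3 = 5 |

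Under 8.1 the pair always spans five sessions, but the starting point varies from 0 to 3.

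**2. Whether Protocol 3 can be followed as written.** It wants a baseline just before the first session, and a second sample both about a day later and after an 11:30 session. The hours from the first session to the 11:30 slots nearest the one-day mark are:

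| First session | Hours to those 11:30 slots | Smallest departure from 24 h |
|---|---|---|
| 11:30 AM | 24 | 0 h |
| 6:30 AM | 5 or 29 | 29 − 24 = 5 h |
| 4:30 PM | 19 or 43 | 24 − 19 = 5 h |
| 9:30 PM | 14 or 38 | 24 − 14 = 10 h |

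Both conditions hold exactly only for an 11:30 start. After a 9:30 PM start, one of them has to give way.

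**3. Later values against the first stimulation.** Assume diagnosis on the day of ictus, aneurysm treatment on post-ictus day 0 to 3 (from the 72-hour statement), enrolment 1 to 5 days after treatment (Protocol 4.1), and stimulation starting on the day of enrolment. First stimulation day = treatment day + enrolment day, so it ranges from 0 + 1 = 1 to 3 + 5 = 8. There are 4 × 5 = 20 combinations.

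- Day 5 falls strictly before the first-stimulation day in 6 of 20: treated day 1, enrolled day 5 after treatment; treated day 2, enrolled day 4 or 5; treated day 3, enrolled day 3, 4 or 5.
- Day 7 falls strictly before it in 1 of 20: treated day 3, enrolled day 5.
- A CT perfusion scan early in the day 3–10 window, if that window is also counted from ictus, can precede a first stimulation that falls later within days 1 to 8.

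These are counts of combinations, not probabilities. A delay from ictus to diagnosis would raise them.

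The figure in Protocol 8.2 shows intervention starting on days 2–4. If those days are post-ictus, the day 5 draw comes 5 − 4 = 1 to 5 − 2 = 3 days after the start, and the day 7 draw 3 to 5 days after. Neither precedes stimulation, although a day 3 scan could still precede a day 4 start. The figure does not state the origin of its starting days.

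**The case against.** The strongest reply is that Protocol 3 already supplies a clean baseline. Its three conditions (before the first stimulation, a day apart, second draw after 11:30) fit together when the first session is at about 11:30, and 8.1 is then the same rule in shorter form. That may well be what was meant. No section says it, however, and a coordinator working from 8.1 alone would be compliant in drawing after one, two or three sessions.

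Several further replies stand:

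- **Late draws.** The day 5 and day 7 samples are optional repeats, and consent must precede any study-specific procedure (Protocol 10.1.1.1). A reader might infer from the counts above that many late enrolees supply unexposed follow-up samples. The documents do not support that: a patient enrolled on day 6 simply has no day 5 sample. An unexposed draw needs consent earlier than the first session, for example because sessions were missed for procedures or unstable vital signs (Protocol 6.1.2). A standard-of-care scan has no such barrier.
- **Start times.** A reader might also infer that most baselines are contaminated, by supposing that first sessions are spread evenly over the four slots. Nothing in the documents gives that distribution.
- **Bias.** Both randomised arms share the same timing rules. The effect is dilution and noise, not a systematic advantage to either arm.
- **Carry-over.** That one to three sessions shift these markers within hours is plausible but not quantified anywhere in the plan.

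**Conclusion.** The two protocol sections conflict and should be reconciled. Under 8.1 as written, a patient may have received 0 to 3 sessions at the baseline draw. Under Protocol 3 as written, the second draw fits only when the first session is near 11:30. How many patients this would affect, and by how much it would shrink the active-arm change, cannot be derived from the documents.

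Separately, an opportunistic CT perfusion scan, in a minority of cases an optional day 5 draw, and only at the extreme a day 7 draw may precede the first stimulation. That statement rests on the timing assumptions listed above, and for the two draws it falls away if the days in the Protocol 8.2 figure are post-ictus.

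A reader might go further and conclude that the before/after objective is lost. It is not. The core pair does not depend on days 5 and 7, and five sessions separate the two draws under 8.1 whatever the start time. This is a minor-to-moderate point on a secondary endpoint collected only when possible, in a pilot of about 40 patients with no statistical hypotheses. It merits correction because the fix is nearly free and a missed pre-stimulation specimen cannot be recovered.

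**What to change.** In Protocol 8.1, state that the baseline blood and CSF samples are drawn before the patient's first stimulation session, whenever that falls, and that the second follows about a day later, after the session in the same clock slot. Five sessions then separate the draws for every patient who misses none, and the baseline always has zero. Align the endpoint table in Protocol 3 with this wording. If the intention is already that patients giving biomarker samples have their first session at 11:30, stating so would also reconcile the two sections. Clarify the repeated CSF sentence at the same time.

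Record on the case report form the number of sessions received before each sample and each CT perfusion scan. State the origin of the day 3–10 window. In the SAP, define biomarker baseline by the first stimulation rather than by Day 1, and count day 5 and day 7 draws and scans as follow-up only if taken after the first stimulation. The vasospasm-window draws stay where they are.

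The cost is wording in two documents and one extra data field. Some draws would fall outside 11:30, and a few scans or samples would leave the follow-up comparison.
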